## 7. STUDY ASSESSMENTS AND PROCEDURES

Study procedures and their timing are summarized in the SOA ([Appendix 1](#)). As protocol waivers or exemptions are not allowed, except for immediate safety concerns, these should be

discussed with the Sponsor immediately upon occurrence or awareness to determine if the subject should continue or discontinue the study drug. Adherence to the study design requirements, including those specified in the SOA, is essential and required for study conduct.

All Screening evaluations must be completed and reviewed to confirm that potential subjects meet all eligibility criteria. The Investigator will maintain a screening log to record details of all subjects screened and to confirm eligibility or record reasons for screening failure ([Section 4.4.1](#)), as applicable. Procedures conducted as part of the subject's routine clinical management (e.g., blood count) and obtained before signing the ICF may be utilized for Screening or Baseline purposes provided the procedure met the protocol-specified criteria and was performed within the timeframe defined in the SOA.

## 7.1. Efficacy Assessments

Efficacy assessments and procedures should be performed in the sequence that is most practical for the site, as long as PROs are performed first, and study drug administration is performed last. The study visits should follow the schedule as much as possible and should occur on the same day of the week. Study drug is also to be administered on the same day. All procedures must occur no more than  $\pm 3$  days from the scheduled date for the study visit.

### 7.1.1. Cardiac Testing

#### 7.1.1.1. Transthoracic Echocardiography

Transthoracic echocardiography (TTE) will be performed at the sites by qualified echocardiographic personnel (technicians or physicians) in accordance with standard echocardiographic clinical practice and with the [Mitchell et al, 2019](#) Guidelines on TTE in adults from the American Society of Echocardiography. The baseline echocardiogram should be performed before administration of study medication. The TTE required will be a standard echocardiographic examination and will include the majority of standard echocardiographic views normally obtained for clinical practice ([Table 4](#)).

Echocardiograms will be recorded to digital media. All digital images should be stored in a DICOM format and sent to the core laboratory for analysis. Detailed image acquisition and transmission will be provided in Echocardiography Participant Scanning Guide and forwarded to all sites.

All echocardiographic measurements will be made at the core laboratory, with initial evaluation performed by experienced ECHO technician, and the overread performed by experienced ECHO cardiologist. Detailed echocardiographic parameters, and their definitions will be provided in Imaging Review Charter (IRC) and reviewed and approved by the sponsor.

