--	---

	

23. A diagnosis of, or presentation consistent with, Lofgren's syndrome.

24. Significant ischemic heart disease, including myocardial infarction within 6 months, unstable angina, or percutaneous transluminal coronary angioplasty (PTCA)/stent within 1 month prior to Screening; or planned coronary intervention (e.g., coronary artery bypass graft [CABG] or PTCA/stent) during the subject's participation in this study.

25. Significant valvular heart disease known or anticipated to require surgical repair or replacement during the subjects' participation in this study.

26. Subject is indicated for a permanent implantable cardioverter defibrillator (ICD) or permanent pacemaker (per Investigator's opinion) but not yet implanted for any reason, or not planned to be implanted, at least 1 week before initiating treatment with study drug. Subjects with temporary pacing devices or external defibrillator devices are excluded under this criterion even if planned for conversion to a permanent device if that cannot occur at least 1 week prior to treatment with study drug.

27. Known or suspected active and untreated/inadequately treated tuberculosis (TB), human immunodeficiency virus (HIV), hepatitis B or C infection. Subjects with latent TB may be enrolled if anti-TB therapy is commenced prior to randomization. Subjects with positive serology for HIV, hepatitis B or C must have an undetectable viral load by real-time polymerase chain reaction (RT-PCR) prior to randomization.

28. Female subjects who are pregnant or breastfeeding or intend to be, during the study.

29. Prior history of any malignancy (not including fully resected squamous cell carcinoma of the skin, fully resected intra-epithelial neoplasia, or carcinoma in situ of the cervix) or lymphoproliferative disorder within the past 5 years.

30. History of severe allergic or anaphylactic reactions to therapeutic proteins or known sensitivity to namilumab or to its inactive components.

31. History of alcohol or drug abuse, in the Investigator's opinion, unless in full remission for greater than 12 months prior to Screening.

32. Abnormal chest radiograph findings that are inconsistent with a diagnosis of sarcoidosis, or are inconsistent with the subjects past medical history, and that warrant further evaluation in the opinion of the Investigator.

33. Any other acute or chronic medical condition that, in the judgment of the Investigator or Sponsor, may increase the risk

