#### **Secondary Endpoints:**

- Other safety endpoints including:
  - Incidence and magnitude of treatment-emergent laboratory abnormalities;
  - Change from baseline in vital signs;
  - Change from baseline in ECG parameters.

- Mean change from baseline in PET maximum standardized update value (SUVmax), SUVmean, and total glycosylation;
- Cumulative arrhythmia burden and hospitalization for cardiac events;
- Mean change from baseline in left ventricular ejection fraction (LVEF) and global longitudinal strain (GLS) on transthoracic echocardiogram (TTE);
- Cumulative oral steroid use, modified glucocorticoid toxicity index (mGTI), and mean change from Baseline in glycosylated hemoglobin (HbA1C);
- Proportion of subjects requiring rescue therapy (either cohort) and proportion of subjects successfully achieving steroid taper without requiring rescue therapy (Cohort A);
- Mean change from baseline in KSQ (General and sub-domains), Fatigue Assessment Scale (FAS), and Subject Global Assessment (SGA);
- Assessments of PPK and E-R relationships for safety and efficacy if data permit.

**Note:** For endpoints defined as mean change from baseline, the primary assessment will be at Week 34.

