18. Systolic blood pressure (SBP)  $< 90$  or  $> 180$  mm Hg; diastolic blood pressure (DBP)  $< 60$  or  $> 110$  mm Hg at Screening.
19. Has documented laboratory-confirmed severe acute respiratory syndrome coronavirus-2 (SARS-CoV-2) infection as determined by polymerase chain reaction (PCR) or other approved clinical testing  $\leq 3$  months prior to randomization.
20. Administration of any fully live virus or bacterial vaccinations within 3 months prior to Screening or administration of non-live or live-attenuated vaccine within 2 weeks of randomization. Note: COVID-19 booster and influenza vaccinations are allowed to be completed during the study.
21. History of mycetoma or fungal respiratory infection.
22. History of or planned solid organ or hematopoietic cell transplantation.
23. A diagnosis of, or presentation consistent with, Lofgren's syndrome.
24. Significant ischemic heart disease, including myocardial infarction within 6 months, unstable angina, or percutaneous transluminal coronary angioplasty (PTCA)/stent within 1 month prior to Screening; or planned coronary intervention (e.g., coronary artery bypass graft [CABG] or PTCA/stent) during the subject's participation in this study.
25. Significant valvular heart disease known or anticipated to require surgical repair or replacement during the subjects' participation in this study.
26. Subject is indicated for a permanent implantable cardioverter defibrillator (ICD) or permanent pacemaker (per Investigator's opinion) but not yet implanted for any reason, or not planned to be implanted, at least 1 week before initiating treatment with study drug. Subjects with temporary pacing devices or external defibrillator devices are excluded under this criterion even if planned for conversion to a permanent device if that cannot occur at least 1 week prior to treatment with study drug.
27. Known or suspected active and untreated/inadequately treated tuberculosis (TB), human immunodeficiency virus (HIV), hepatitis B or C infection. Subjects with latent TB may be enrolled if anti-TB therapy is commenced prior to randomization. Subjects with positive serology for HIV, hepatitis B or C must have an undetectable viral load by real-time polymerase chain reaction (RT-PCR) prior to randomization.
28. Female subjects who are pregnant or breastfeeding or intend to be, during the study.

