#### **7.1.2. Radiographic Assessments**

Details for the [18-F] FDG-PET/CT imaging requirements, scanner validation, procedures for phantom image capture, and data transfer requirements are described in the Participant Scanning Guide provided to all Investigators and collaborating radiology units.

To avoid unnecessary radiation, it is recommended all other Screening activities need to be completed prior to PET scans for eligibility. In all cases, the lowest radiation dose approach for imaging should be used. Subjects will undergo up to 3 [18-F] FDG-PET/CT scans; cumulative radiation exposure from these scans will range from 22.2 mSv to 41.7 mSv, depending primarily on CT technique used.

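### The baseline echo is not tied to a device implanted during Screening, so in probably few subjects the LVEF/GLS change may include a device effect

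*Combined protocol and SAP*

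**What the plan says.** Four parts of the protocol bear on this.

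- **Echo timing.** Section 7.1.1.1 says: "The baseline echocardiogram should be performed before administration of study medication". It does not mention device status. The Schedule of Assessments (Appendix 1) has one pre-dose echo, in the Screening column (Day -42 to -1), and none at the Baseline visit. Follow-up echoes are at Weeks 10, 22 and 34.
- **Device timing.** Exclusion 26 (Section 4.2; the synopsis repeats it) removes a subject with an indication for a permanent ICD or pacemaker if the device is not implanted, or "not planned to be implanted, at least 1 week before initiating treatment with study drug". Its second sentence excludes temporary devices "even if planned for conversion to a permanent device if that cannot occur at least 1 week prior to treatment with study drug".
- **Which echo may serve.** Under Section 7, routine-care procedures done before consent "may be utilized for Screening or Baseline purposes provided the procedure met the protocol-specified criteria" and fell within the scheduled timeframe. Section 7.1.2 adds that "it is recommended all other Screening activities need to be completed prior to PET scans for eligibility", which tends to put the echo early.
- **Use of the data.** Section 2.2 lists mean change from baseline in LVEF and GLS as a secondary endpoint, with Week 34 as the primary assessment. Sections 8.4 and 8.5 mention sensitivity analysis for missing data and model-based estimates. They say nothing about device status.

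**The concern.** A change from baseline can be read as a treatment effect only if the two measurements were taken under comparable conditions. A device that paces alters how the ventricle is activated, so an echo in native conduction and one in paced rhythm may differ for reasons unrelated to inflammation or study drug.

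The situation is plausible here. Section 1.2 names conduction abnormalities and ventricular arrhythmia as manifestations of cardiac sarcoidosis, and Exclusion 26 is written with implantation before dosing in view.

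LVEF and GLS change is the listed endpoint that answers the cardiac-function objective. Cohort B has a single arm, so a device effect and a drug effect would appear as one number. In Cohort A, randomization balances such subjects on average, but there are only 10 per arm and Section 5.4 names no stratification factor.

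**Working it through.** The plan gives no figure to reproduce: Section 8.1 states that the sample size has no formal power basis. The check is day arithmetic on the schedule, followed by an illustration with assumed inputs.

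**1. Can a compliant baseline echo precede a compliant implant?** The schedule has no Day 0.
- Earliest Screening echo: Day -42, which is 42 days before Day 1.
- Latest implant under Exclusion 26: 7 days before Day 1, which is Day -7.
- Largest gap: 42 - 7 = 35 days.

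**2. Are all follow-up echoes after the device?** Days from a Day -7 implant, subtracting 1 for the missing Day 0:
- Week 10 (Day 71): 71 + 7 - 1 = 77 days.
- Week 22 (Day 155): 155 + 7 - 1 = 161 days.
- Week 34 (Day 238): 238 + 7 - 1 = 244 days.

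An earlier implant lengthens these intervals, so every scheduled follow-up is post-device.

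**3. Does another rule close the gap?** Nothing in the protocol asks for the echo after the implant, for a repeat echo, or for device status in the LVEF/GLS analysis. Exclusion 1 concerns cardiac hospitalization in the 30 days before Screening, so it does not reach an implant during Screening.

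**4. Illustrative size (assumed inputs).** Let k of 10 subjects in a group be affected, each with an LVEF step of s points in the same direction. The group mean change moves by k × s / 10.

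| k | s = 2 | s = 5 | s = 10 |
|---|---|---|---|
| 1 | 0.2 | 0.5 | 1.0 |
| 2 | 0.4 | 1.0 | 2.0 |

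A device that does not pace may add no step, and steps in opposite directions would partly cancel. Neither k nor s is in the documents.

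**5. Chance imbalance in Cohort A.** If 2 of the 20 subjects were affected and the split is 10:10, the second falls in the same arm as the first with probability 9/19 = 47%. The between-arm difference would then shift by the k = 2 row. Otherwise (10/19 = 53%) there is one in each arm, and equal steps cancel.

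**The case against.** The strongest reply is that the affected group is narrow and the harm is not quantified in the documents.

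- **Few subjects.** Section 1.2 says many patients already have a pacemaker or ICD; for them every echo is post-device. Exclusion 1 removes recent cardiac hospitalizations, and Exclusion 16 removes a history of LVEF of 30% or less or NYHA class III or IV. What remains is a device placed during Screening, after the echo. This stands.
- **Unknown effect.** No passage says that a device changes LVEF or GLS, by how much, or in which direction. This stands too.
- **Existing records.** Footnote l of the schedule collects concurrent procedures from informed consent and sends procedures before randomization to the medical history. A 12-lead ECG is scheduled at every visit that has an echo. The affected subjects can therefore largely be identified already. This shapes the fix.
- **Unseen documents.** The Imaging Review Charter, the echo scanning guide and the detailed SAP were not available and may address the point. However, the protocol itself sets the baseline timing, and that rule does not mention devices.

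A reader might infer that one or two such subjects could create or hide a treatment difference. The documents do not support that. They give no SD, confidence-interval width or meaningful difference against which to judge a shift, and Section 8.5 plans no efficacy hypothesis test and treats nominal p values as descriptive.

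A reader might also infer that the protocol expressly invites implants during Screening, or that resynchronization is involved. Admission is only inferred from an exclusion criterion, and that criterion names only an ICD or a permanent pacemaker.

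**Conclusion.** The gap is real on the text. A subject can comply with Section 7.1.1.1, the schedule and Exclusion 26 and still have a baseline echo up to 35 days before a new device, with all three follow-up echoes after it. Where the device paces, the LVEF and GLS change may include a device effect. Cohort B cannot separate that from drug, and Cohort A balances it only on average.

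The number affected is probably small, and the size and direction of the effect are unknown. The 0.2 to 2.0 point range rests wholly on the assumed k and s. The primary safety endpoint is not touched. The point is of low to moderate priority: a comparability problem in one descriptive secondary endpoint that is cheap to avoid or to display.

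**What to change.** **Protocol, Section 7.1.1.1.** State that when a permanent device implant is already planned during Screening, the Screening echo used as baseline is acquired after the implant and before first dose. If the echo was done before the indication arose, do not require a second one; flag the subject instead.

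**Detailed SAP.** Identify subjects whose device or paced status differs between the baseline echo and a follow-up echo, using the implant date in the concurrent-procedure or medical-history record and the 12-lead ECGs from the same visits. Show LVEF and GLS change with and without these subjects, by cohort. Section 8.8 requires the SAP to be signed only before database lock, so this can be pre-specified there.

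**Cost.** A scheduled test is reordered for the subjects concerned, and one display is added. A pre-implant routine-care echo could not serve as baseline when an implant is planned, and the echo may fall later than the order recommended in Section 7.1.2. The ECG tracings would need to be read for pacing, since Section 7.2.3 lists only heart rate, intervals and the QRS complex. Subjects implanted after an echo already done keep a pre-device baseline; the display exposes this but does not correct it. The device timing rule in Exclusion 26 stays as it is.

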**Table 4. Summary of Standard Echocardiographic Views**

Echocardiographic view	Images
Parasternal long axis view	2-D image for septal and posterior wall thickness, volume, and ejection fraction measures, LA size/volume M-mode images

**Table 4. Summary of Standard Echocardiographic Views**

Echocardiographic view	Images
	Color flow Doppler
Parasternal short axis view, papillary muscle	2-D image for septal and posterior wall thickness
Apical 4-chamber view	2-D images for volume and ejection fraction measures, LA size/volume, and RV function Color flow Doppler for assessment of mitral regurgitation Global longitudinal strain Doppler Tissue Imaging of mitral annular velocities Mitral inflow pulsed Doppler

Additional images may be acquired if the anatomy is not well visualized on the required views ([Table 5](#)).

**Table 5. Additional Imaging Parameters**

Echo Views	Parameters
Parasternal Long Axis View	

• 2D at normal depth

• Color Doppler of MR and AR

Parasternal Short Axis View	

• 2D of the LV at Mid-Papillary Muscle level

Apical 4 Chamber View	

• 2D Standard 4 Chamber view

• 2D optimize view of the LV

• 2D with optimize view of the RV, Reduce the depth and focus only on the RV

• Color Doppler of MR

• Color Doppler of TR

• CW Doppler of TR jet

• M-Mode of Tricuspid Annular Motion or TAPSE

• Tissue Doppler of Tricuspid lateral annulus

Apical Long Axis View	

• 2D of LA and LV, LVOT

• Color Doppler for MR

Apical 2 Chamber View	

• 2D with LV and LA optimized

• Color Doppler of MR

#### **7.1.1.2. Wearable Device for Arrhythmia Assessment**

An ambulatory ECG monitor (ePatch) will be placed on the subject at each visit (from Screening through Week 30). The device is made up of a sensor which is placed in an electrode patch. Together, they are placed on the subject. The ePatch will continuously record a 1-channel ECG. Subjects will be monitored via ePatch for 10 consecutive days; one patch will be worn for 5 days, then the patch will be replaced by the subject, and the second patch will be worn for an additional 5 days. After 10 days of wearing the device, the Subject should remove it and return it to the investigational site at their next clinic visit. The site will upload the data as described in the ePatch acquisition guide and give the subject a new device. The initial recording period during screening provides an opportunity for the software system that will be used to interpret the data during treatment to learn the Subjects usual physiology prior to commencing study drug. A detailed manual (ePatch Acquisition Guide) describing affixation and removal of the device, and requirements for upload of recorded data will be provided and all site staff will be trained on the use of the ePatch device.

#### **7.1.2. Radiographic Assessments**

Details for the [18-F] FDG-PET/CT imaging requirements, scanner validation, procedures for phantom image capture, and data transfer requirements are described in the Participant Scanning Guide provided to all Investigators and collaborating radiology units.

To avoid unnecessary radiation, it is recommended all other Screening activities need to be completed prior to PET scans for eligibility. In all cases, the lowest radiation dose approach for imaging should be used. Subjects will undergo up to 3 [18-F] FDG-PET/CT scans; cumulative radiation exposure from these scans will range from 22.2 mSv to 41.7 mSv, depending primarily on CT technique used.

#### **7.1.2.1. [18-F] Fluorodeoxyglucose-Positron Emission Tomography/Computed Tomography**

All subjects will undergo whole-body head to mid-thigh [18-F] FDG-PET/CT imaging with a reconstructed resolution of  $\leq$ 5mm during Screening and at Week 34. Subjects in Cohort A will receive an additional scan at Week 22, and subjects in Cohort B will receive an additional scan at Week 10. Timepoints for imaging are specified in the SOA ([Appendix 1](#)). All subjects must adhere to a low carbohydrate/low calorie diet 24 hours prior to the PET scan; the treating Investigator should discuss the appropriate diet options with subjects, see [Appendix 11](#) for diet recommendations. Details of the scan requirements and procedures are contained in the Participant Scanning Guide. At Screening, the scan may be interpreted locally to confirm evidence of disease activity consistent with active CS; however, all scans are subject to central read for the purposes of eligibility. Only central imaging interpretation will be accepted for eligibility determination.

A PET/CT scan conducted as part of the usual clinical management of the subject (e.g. assessment for suspected CS) within 2 weeks prior to informed consent may be considered/assessed for use in place of the Screening PET/CT exam if the scan can be uploaded to the central imaging vendor for central read and the OCS dose has not changed in the 4 weeks prior to the scan. If this PET/CT scan is deemed unable to be assessed, is of insufficient quality on central read, or was performed more than 2 weeks prior to informed consent, the PET/ CT scan must be repeated and performed as part of screening, per protocol. The central read will determine final study eligibility compared to local interpretation. For subjects considered for inclusion into Cohort A, high-dose OCS may be commenced at any time after a potentially eligible PET/ CT scan has been performed including before informed consent (e.g. after diagnosis of CS, it may be likely to start high dose OCS as part of the usual care of CS, before entering into Screening and signing informed consent); however, if the OCS dose is changed to  $>10$  mg/ day of prednisone (or equivalent), and the PET/CT scan needs to be repeated (i.e. performed as part of usual management and unable to be assessed or insufficient quality on central read) then the subject will be ineligible for inclusion. If the OCS dose commenced as part of usual care, before informed consent, is not within the protocol-defined range of 25-60 mg/ day prednisone (or equivalent), it should be adjusted to be within the protocol-defined range as soon as is practical after the subject has signed informed consent and no later than the time the subject is randomized/enrolled.

Subjects with glucose levels above 11 mmol/L (200 mg/dL) should have their scan delayed or be rescheduled as appropriate. The blood glucose level measured prior to the radiotracer administration should be recorded in the image transmittal form. Subjects will have the radiotracer administered through an IV line, after which they will be positioned comfortably in a supine position as stated in the Participant Scanning Guide.

Screening, Week 10 (Cohort B only), Week 22 (Cohort A only), and Week 34 scans will be assessed as follows.

- Change in the SUVmax – mean change from Baseline;
- Mean change in SUVmean from Baseline;
- Mean change in Total Glycosylation vs Baseline;
- Mean change in SUVmax in extracardiac regions of interest;
- Percentage lesion resolution rate in the cardiac and extracardiac regions of interest, to an SUV of 1.2 or less. For exploratory purposes, different sensitivity thresholds will be applied to define resolution.

Total radiation exposure for study subjects will be minimized as far as possible as follows:

- [18-F] FDG-PET/CT scans should ideally be performed after subjects have completed other Screening requirement successfully;
- Lowest dose of injectable radioisotope should be used per the guidance in the Participant Scanning Guide;
- Poor quality scans will not be repeated for study purposes, unless indeterminate for study inclusion.

Subjects will undergo up to 3 [18-F] FDG-PET/CT scans; cumulative radiation exposure from these scans will range from 22.2 mSv to 41.7 mSv, depending primarily on CT technique used.

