#### **3.1.4.1. Rescue Visit**

During the study, if a subject requires rescue therapy outside of a required study visit, the Investigator should schedule a Rescue Visit to confirm the need for rescue therapy. Prior to providing rescue therapy, and dependent on the subject's clinical condition, the Investigator should attempt to complete all efficacy assessments that would be required during a Week 10 (Cohort B), or Week 22 (Cohort A) in-clinic visit as outlined in [Appendix 1](#). The Rescue Visit should be documented on the appropriate eCRF page.

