## 6.4. Rescue Therapy

The clinical status of a subject in either Cohort may deteriorate. The Investigator should instruct subjects to contact study staff immediately if they feel their symptoms or signs of sarcoidosis, particularly of their cardiac disease, are worsening.

The Investigator may assess that the clinical deterioration is due to progression of CS and may wish to provide rescue therapy. In this circumstance, increased OCS dosing at the lowest effective increment with the shortest duration is the preferred option so that integrity of the study may be preserved. Alternatively, the change in regimen may be increased dosing of a current IST or the addition of a new one.

In this protocol rescue therapy is defined as any of the following:

- (Cohort A) Failure of the OCS taper, i.e., the subject requires an increase in OCS dose during the protocol-specified taper ([Appendix 8](#));
- (Cohort A) Protocol-specified dose levels cannot be reached by the pre-specified timepoints ([Appendix 8](#));
- (Cohort A) Increase in OCS dose above 10 mg/day prednisone, or equivalent, after the taper is complete;
- (Cohort B) Increase in OCS dose above 10 mg/day prednisone, or equivalent, at any time;
- (Either Cohort) Start of a new IST or change in dose or frequency of a current IST;
- (Either Cohort) Use of a prohibited medication to treat sarcoidosis-related signs or symptoms.

The following do not constitute rescue therapy:

- Use of OCS for up to 14 days or less for treatment of an event not related to sarcoidosis, e.g., an acute allergic reaction, acute contact dermatitis;
- Use of inhaled OCS or bronchodilators, e.g., long-acting beta agonists or long-acting muscarinic agonists.

Prior to initiating rescue therapy in a subject who is not hospitalized, an unscheduled visit should be performed; see [Sections 3.1.4](#) and [3.1.4.1](#) for details.

If it would not adversely affect a subject's safety or wellbeing, PET/CT and TTE should be performed before initiation of rescue therapy.

Cohort A subjects should resume the protocol-specified steroid taper ([Appendix 8](#)) at the earliest opportunity based on the Investigator's clinical judgement.

The Medical Monitor must be contacted if rescue therapy is initiated, and the reason(s) should be captured in source records and in the CRF.

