### Informed Consent

Prior to starting participation in the study, each subject will be provided with a study specific ICF giving details of the study drugs, procedures, and potential risks of the study. Subjects will be instructed that they are free to obtain further information from the Investigator (or designee) and that their participation is voluntary, and they are free to withdraw from the study at any time.

Subjects will be given an opportunity to ask questions about the study prior to providing consent for participation.

Subjects or their legally authorized representative will be required to sign a statement of informed consent that meets the requirements of local regulations, ICH guidelines, and the IRB or study center, where applicable. The subject will be given a copy of the signed ICF, and the original will be maintained with the subject's records.

Subjects must be re-consented to the most current version of the ICF(s) during their participation in the study.

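### The stated maximum of 3 FDG-PET/CT scans and 22.2–41.7 mSv leaves no room for the pre-rescue scan that the protocol also requests, so a rescued completer can have 4

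*Combined protocol and SAP*

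**What the plan says.** **Stated maximum.** Section 7.1.2.1 closes with "Subjects will undergo up to 3 [18-F] FDG-PET/CT scans; cumulative radiation exposure from these scans will range from 22.2 mSv to 41.7 mSv". Section 7.1.2 gives the same count and the same range, "cumulative radiation exposure from these scans will range from 22.2 mSv to 41.7 mSv, depending primarily on CT technique used".

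**Scheduled scans.** Section 7.1.2.1 has all subjects scanned at Screening and Week 34, and adds one mid-study scan: "Cohort A will receive an additional scan at Week 22, and subjects in Cohort B will receive an additional scan at Week 10". The Schedule of Assessments (Appendix 1) agrees.

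**Scan before rescue.** Section 6.4 says "If it would not adversely affect a subject's safety or wellbeing, PET/CT and TTE should be performed before initiation of rescue therapy". Section 3.1.4.1 covers rescue that arises between scheduled visits. It says that before rescue is given, if the subject is well enough for it, "the Investigator should attempt to complete all efficacy assessments that would be required during a Week 10 (Cohort B), or Week 22 (Cohort A") visit. Those are each cohort's mid-study PET visits.

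**Repeat scans.** Section 7.1.2.1 says "Poor quality scans will not be repeated for study purposes, unless indeterminate for study inclusion".

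**Scans assessed.** Section 7.1.2.1 introduces its PET outputs with "Screening, Week 10 (Cohort B only), Week 22 (Cohort A only), and Week 34 scans will be assessed as follows". A pre-rescue scan is not in that list.

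**Consent.** Appendix 6 says "each subject will be provided with a study specific ICF giving details of the study drugs, procedures, and potential risks of the study".

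**The concern.** The count is worded as a maximum per subject. In Section 7.1.2.1 it follows directly on the measures for keeping radiation low. Yet the scheduled scans use up the whole allowance, and two other sections ask for another scan in a situation the protocol plainly expects: use of rescue is a secondary endpoint in both cohorts, and Section 6.4 defines it broadly. The sections cannot all be right for a subject who is rescued and completes the schedule.

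At stake is a participant-risk figure. Sites, IRBs and whoever drafts the consent form are likely to take the scan count and radiation range from these two sections. There is also a smaller gap in data handling. The protocol does not say whether a pre-rescue scan goes to central read or how it will be reported.

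**Working it through.** **Step 1. Reproduce the stated count** (Section 7.1.2.1 and Appendix 1).

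| Cohort | Screening | Week 10 | Week 22 | Week 34 | Total |
|---|---|---|---|---|---|
| A | 1 | – | 1 | 1 | 3 |
| B | 1 | 1 | – | 1 | 3 |

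Both totals equal the stated maximum of 3. The mSv range cannot be derived independently, because no per-scan dose is given.

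**Step 2. Look for a substitution rule.** Sections 3.1.4.1, 6.4 and 7.1.2.1 and the Appendix 1 footnotes contain nothing that lets a pre-rescue scan replace the Week 10, Week 22 or Week 34 scan. Rescue does not end participation: Section 6.4 expects rescued Cohort A subjects to return to the taper, and the Week 34 scan is for everyone.

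**Step 3. Count with one pre-rescue scan.** 3 scheduled + 1 = 4.

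**Step 4. Radiation, assuming the range covers 3 scans of equal dose.**
- Per scan: 22.2 / 3 = 7.4 mSv; 41.7 / 3 = 13.9 mSv.
- Four scans: 4 × 7.4 = 29.6 mSv; 4 × 13.9 = 55.6 mSv.
- Relative increase: 4/3 − 1 = 33%. At the upper end, 55.6 − 41.7 = 13.9 mSv more.
- Mean dose per scan at which four scans reach the stated upper figure: 41.7 / 4 = 10.4 mSv. Below that, the count is exceeded but 41.7 mSv is not.

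**Step 5. When the count does not rise.**
- Rescue falls at a scheduled PET visit, so one scan serves both purposes.
- The conditional pre-rescue scan is not done.
- A later scheduled scan is missed.
- A usual-care scan served as the Screening scan (Sections 3.1.1 and 7.1.2.1). The subject still has 4 scans in all, but the study performs only 3 of them.

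**Step 6. Repeat at Screening.** A study-performed screening scan that is indeterminate for inclusion may be repeated, which could add one more scan. This does not apply to every unreadable scan. If the unreadable scan came from usual care, its repeat is the first study-performed scan. If steroid dose has by then gone above 10 mg/day of prednisone or equivalent, Section 7.1.2.1 makes the subject ineligible. I give no radiation figure for this case, because it stacks several conditions on the equal-dose assumption.

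**The case against.** The best reply is that the sentence describes scheduled scans only, that the pre-rescue scan is conditional in both places where it appears, and that in a study of about 30 subjects few will be affected. The conditionality stands: 4 is a foreseeable count, not one for every rescued subject. The reading as scheduled scans only is not in the text, which gives a maximum per subject without qualification. If that is what is meant, saying so and giving the contingent figure is the correction needed.

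Some stronger readings are tempting, and the documents do not support them.

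- A reader might infer that the pre-rescue scan serves no purpose, since it is missing from the list of assessed scans. Section 3.1.4.1 places it among the efficacy assessments, at a visit held to establish that rescue is needed. What is missing is a rule on central reading and reporting.
- A reader might infer that 41.7 mSv is an exposure limit that the protocol breaches. Both sections give the range as a description of the exposure from up to 3 scans. It is incomplete for a fourth scan, but not shown to be wrong for three.
- A reader might infer that subjects are misinformed at consent. The consent form is not among the documents reviewed, so this can only be checked.
- A reader might extend the point to the analysis of Week 34 values after rescue. That is a separate question. Section 8.5.1 leaves efficacy methods to an SAP whose text is not in the document reviewed, and the scan count has no bearing on it.

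**Conclusion.** The contradiction holds. Sections 7.1.2 and 7.1.2.1 give a maximum of 3 scans, and the protocol's own procedures lead to 4 for a subject who is rescued away from a scheduled PET visit, has the pre-rescue scan and completes the schedule. The count rests on no assumption beyond those conditions.

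The radiation figure of 29.6–55.6 mSv rests on equal dose per scan, which the documents neither state nor exclude. On that basis exposure is one third higher than stated, and whether it passes 41.7 mSv depends on CT technique. The number of subjects affected cannot be derived without a rescue rate.

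The figure should be corrected because it describes a risk to participants and correcting it is cheap. The point does not undermine the design or the primary safety objective.

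**What to change.** 1. Reconcile Sections 3.1.4.1 and 6.4 with Sections 7.1.2 and 7.1.2.1, in one of two ways: restate the maximum scan count and radiation range to include a pre-rescue scan and a repeat screening scan, or state when a rescue scan and a scheduled scan count as the same scan. The choice of rule is the sponsor's. Under either, say whether the request applies to every rescue or once per subject, since the maximum depends on it.
2. Say whether the count covers all scans or only study-performed ones, given that a usual-care scan may serve as the Screening scan.
3. Check that the exposure figure in the consent form matches the corrected text.
4. State whether pre-rescue scans are centrally read, and report them in a separate listing with study day. They should not enter the scheduled-visit mean-change summaries: they are triggered by an event, fall on varying days and exist only for rescued subjects.

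**Cost.** Corrected sentences in two sections, a cross-reference in two more, one listing and a consent form check. The stated maximum exposure may rise, and Appendix 6 requires IRB approval of the amendment before it takes effect.
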